8 STUDY CONDUCT

8.1 Treatments to be Administered

The investigational product in this study is ciclesonide MDI (supplied as Alvesco Inhalation Aerosol, 160 μ g) or a matching placebo MDI; all patients will also receive standard supportive COVID-19 care. The investigational product will be self-administered by the patient BID (2 actuations in the AM and 2 actuations in the PM) for 30 days. During the initial screening/enrollment/randomization visit, patients will be provided with investigational product for the duration of the 30-day treatment period and will be instructed on how to appropriately self-administer a MDI. For patients in the ciclesonide arm, the total daily dose will be 640 μ g (320 μ g BID). Patients will be instructed to rinse their mouth with water following inhalation of investigational product.

8.2 Method of Assigning Patients to Treatment Groups

Following signature of the ICF, patients meeting inclusion/exclusion criteria will be randomly assigned (1:1) to treatment with ciclesonide MDI 320 μ g BID plus standard supportive care or placebo MDI BID plus standard supportive care. The randomization schedule will be generated by the contract manufacturing organization and incorporated into the labeling of kits. Randomization will be done in blocks of 6 with 3 active and 3 placebo kits randomized within each block. Sites will be supplied with kits in groups of 6 according to these predetermined blocks. Assignment of kits to patients at a site will be done sequentially with patients receiving the next available kit in the block of kits when they have met the necessary criteria and are ready to be randomized.

All patients will be assigned a unique patient number during the screening/enrollment/randomization visit. After a patient number has been assigned, the number will not be reused even if the patient withdraws before receiving any study drug.

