3.3 Rationale for Dose Selection and Treatment Duration

The dose of ciclesonide selected for use in this study is 320 μ g twice daily (BID), which is the currently approved highest recommended starting dose for Alvesco Inhalation Aerosol (Alvesco[®] Inhalation Aerosol US prescribing information, 2019). Patients will be instructed to self-administer Alvesco Inhalation Aerosol (hereafter referred to as ciclesonide MDI) or placebo MDI at a frequency of BID concurrently with standard supportive care for 30 days. The duration of treatment is consistent with the limited information available regarding time to discharge for patients in China without hypoxemia or respiratory distress (mean time to discharge 17 ± 4 days) (Pan et al, 2020).

Because there are no proven or approved treatments for COVID-19, all patients will also receive standard supportive care according to the treating facility's standard.

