6 PATIENT ELIGIBILITY AND WITHDRAWAL CRITERIA

6.1 Number of Patients

Approximately 400 patients (200 in each arm) will be randomized. A sample size justification is provided in section 10.1.

It is anticipated that patients will be enrolled at up to 15 study sites in the United States.

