10 STATISTICAL EVALUATION

As a companion to this protocol and in an effort to provide a more detailed explanation of the statistical methodology to be used for this study, a SAP will be finalized prior to locking the database and before unblinding the randomization. Any changes in the statistical methods described in this protocol that occur prior to unblinding will be documented in the SAP and will not require a protocol amendment.

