10.7 Analysis of Efficacy Data

10.7.1 Primary Efficacy Endpoint

The primary efficacy variable is time to alleviation of COVID-19-related symptoms of cough, dyspnea, chills, feeling feverish, repeated shaking with chills, muscle pain, headache, sore throat, and new loss of taste or smell, defined as symptom-free for a continuous period of \geq 24 hours (ie, \geq 3 AM/PM assessments) by day 30. The primary analysis will be based on the ITT population (all randomized patients). To improve the precision of treatment effect estimation and inference, baseline covariate adjustments will be made for gender, age, race, and body mass index, as these are known COVID-19 risk factors. A Cox proportional hazards model will be used to allow for inclusion of these additional covariates. The median time to event and 95% confidence intervals will be summarized by treatment arm, and Kaplan-Meier estimates of the survival curves will also be generated.

The SAP will describe how missing data will be handled in the primary analysis. In addition, a sensitivity analysis for the primary endpoint will be conducted using a tipping point analysis that will systematically and comprehensively vary assumptions about the missing outcomes on the treatment arms. Details will be provided in the SAP.

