10.7.2 Secondary Efficacy Endpoints

The secondary efficacy endpoints of percentage of patients with hospital admission or death by day 30; all-cause mortality by day 30; COVID-19-related mortality by day 30; percentage of patients with subsequent emergency department visit or hospital admission for reasons attributable to COVID-19 by day 30; and percentage of patients with alleviation of COVID-19-related symptoms of cough, dyspnea, chills, feeling feverish, repeated shaking with chills, muscle pain, headache, sore throat, and new loss of taste or smell, defined as symptom-free for a continuous period of \geq 24 hours (ie, \geq 3 AM/PM assessments) by day 7, by day 14, and by day 30 will be analyzed using a logistic regression model. To improve the precisions on treatment effect estimation and inference, baseline covariate adjustments will be made for gender, age, race, and body mass index, as these are known COVID-19 risk factors. Analysis of the secondary efficacy endpoint of time to hospital admission or death will be performed using the same method as that used for the primary efficacy endpoint. The secondary efficacy endpoint of change from baseline in oxygen saturation levels will be summarized descriptively at all time points captured in the eDiary. The secondary efficacy endpoint of change from baseline in COVID-19 viral load in nasopharyngeal sample at day 30 will be summarized descriptively.

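### Kits are blocked by site, but the Cox and logistic models leave site out, so the tests are conservative and lose power if recovery differs between sites

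*Combined protocol and SAP*

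**What the plan says.** Section 8.2 describes the allocation in three steps. The schedule is blocked: "Randomization will be done in blocks of 6 with 3 active and 3 placebo kits randomized within each block". The blocks are shipped whole: "Sites will be supplied with kits in groups of 6 according to these predetermined blocks". They are used in order at each site: "Assignment of kits to patients at a site will be done sequentially with patients receiving the next available kit in the block of kits". The word stratified does not appear.

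Section 6.1 gives about 400 patients and adds: "It is anticipated that patients will be enrolled at up to 15 study sites in the United States".

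For the primary Cox model, section 10.7.1 says "baseline covariate adjustments will be made for gender, age, race, and body mass index, as these are known COVID-19 risk factors". For the secondary logistic models, section 10.7.2 says "To improve the precisions on treatment effect estimation and inference, baseline covariate adjustments will be made for gender, age, race, and body mass index". Time to hospital admission or death uses the primary method. Nowhere is site a stratum, covariate or random effect.

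Section 3.3 says "all patients will also receive standard supportive care according to the treating" facility's standard, so background care may differ between sites. No separate SAP was among the supplied text. Section 10 allows the SAP to change methods: "Any changes in the statistical methods described in this protocol that occur prior to unblinding will be documented in the SAP", without a protocol amendment.

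**The concern.** When arms are balanced within sites, differences between sites largely cancel out of the treatment comparison. A model without site still counts those differences as noise, so its standard error is larger than the true sampling variation. The test then rejects too rarely, both under the null and under a real effect. The error runs one way: it costs power and does not inflate false positives.

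The protocol adjusts for covariates expressly to gain precision, yet omits the one factor that its own allocation balances. The stakes are highest where power is not in surplus. That is the case if the true effect is smaller than planned, if drop-out uses up the inflation from 232 to 400 patients, or for alleviation by day 14. That endpoint is second of 11 in the fixed sequence of section 10.7.3, so failing there stops formal testing of nine more.

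**Working it through.** **1. The plan's own figure.** Inputs from section 10.1: hazard ratio (HR) about 1.58, α = 0.05, power 90%. Two-sided Schoenfeld: events = 4(1.960 + 1.282)² / (ln 1.58)² = 201. This reproduces the stated 201; the one-sided version gives 164, so the plan is two-sided.

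With exponential times and 30 days of follow-up, the event probabilities are 1 − 0.5^(30/7) = 0.949 and 1 − 0.5^(30/11) = 0.849, mean 0.899. With 400 patients that is about 360 events and 99.0% power at HR 11/7 = 1.57, before any site variation.

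**2. Balance within site.** Complete blocks add no imbalance. An open block with m kits used adds at most min(m, 6 − m) ≤ 3. The average site has 400/15 ≈ 27 patients, or 27/6 ≈ 4.4 blocks. This is site-stratified randomisation in effect, provided that kits are used in order as section 8.2 requires.

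**3. Assumed between-site SD.** This is the SD of log recovery rate left after the four covariates. It is not in the documents, so 0, 0.25, 0.5 and 0.75 were used. With the 11-day placebo median, 95% of site medians lie in 11 × exp(±1.96 × SD): about 7–18, 4–29 and 3–48 days for the three non-zero values. The last is extreme.

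**4. Main simulation.** 15 sites of unequal size; blocks of 6 within site; exponential recovery; normal site effects; censoring at day 30. Both models include gender, age, race and body mass index (assumed log-HRs 0.15 to 0.2 in size). Sites with fewer than 12 patients are pooled. There were 20,000 null trials (Monte Carlo SE about 0.15 points) and 5,000 per power setting (SE 0.2–0.7 points). Each cell gives the result without site / with site.

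| Setting | SD 0 | SD 0.25 | SD 0.5 | SD 0.75 |
|---|---|---|---|---|
| Cox, type I error, N=400 | 5.5 / 5.4% | 4.8 / 5.2% | 3.7 / 5.1% | 2.6 / 5.1% |
| Cox, power, N=400, HR 1.57 | 98.6 / 98.2% | 98.2 / 98.2% | 96.6 / 97.9% | 92.2 / 97.3% |
| Day-14 logistic, power, N=400, HR 1.57 | 92.6 / 93.0% | 91.7 / 92.4% | 87.1 / 90.1% | 79.4 / 86.0% |
| Cox, power, N=400, HR 1.3 | 68.9 / 66.7% | 65.8 / 65.8% | 57.2 / 64.6% | 46.7 / 62.8% |
| Cox, power, N=232, HR 1.57 | 90.3 / 88.3% | 88.0 / 87.5% | 81.5 / 85.6% | 71.4 / 83.2% |

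At N=232 the two Cox models break even at SD about 0.3 (86.1% each; 10,000 trials). If covariate means also differ between sites (by SD 0.5 of a covariate SD), at residual site SD 0.5 type I error is 3.9% against 5.0% and power at HR 1.3 is 57.0% against 63.5%, so the picture is unchanged.

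**5. Separate check.** A second program, without covariates or pooling (4,000 null and 2,500 alternative trials), used site SD 0, 0.3, 0.5 and 0.8 with N=400:

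- Type I error of Cox without site: 5.0, 4.1, 3.1, 2.2%; stratified: 5.1, 4.3, 4.9, 5.0%.
- With central blocks not tied to site, Cox without site stays at 4.5–5.8%. The conservatism therefore comes from the site-level blocking.
- Power at HR 1.57: 99.1, 98.2, 96.8, 91.3% without site; 98.7, 98.5, 98.4, 97.3% stratified.

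**6. Effect estimate.** At SD 0.5 and the design HR, the mean estimated HR is 1.49 without site and 1.57 stratified. This is mainly a change of target (averaged over sites against within site), not plain bias.

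**The case against.** The strongest reply is that this hardly touches the planned primary analysis. At N=400 and the design HR, power without site stays above 90% even at SD 0.75, and type I error is protected. That stands.

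The benefit also rests on an unknown. Entry criteria are uniform and all sites are in the United States. Facility-standard care shows that care may differ, not that recovery differs much. SD 0.5, where losses begin to matter, is already a wide spread of site medians. A further null run of 20,000 trials gave type I error without site of 5.3, 5.1, 4.6 and 4.5% at SD 0, 0.15, 0.25 and 0.3, which is a small effect. At N=232, stratifying loses power below SD about 0.3. All of this stands and limits the weight of the point.

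The larger losses come from scenarios that the plan does not adopt. HR 1.3 is not in the documents, and falling from 400 to 232 means losing 168/400 = 42% of the information, although censored patients still contribute time. That is fair. However, section 10.1 calls its inputs best estimates amid much uncertainty, and the day-14 loss at SD 0.5 (87.1% against 90.1%) arises at the design HR and full size.

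A within-site HR is also further from the summaries in sections 4.3.1 and 4.3.2, a difference in survival distributions and a difference in response probabilities. This needs a sentence in the SAP, but the four-covariate models are already conditional. Finally, the SAP may already include site; the absence is shown only for the protocol text.

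**Conclusion.** The point holds. Allocation is blocked by site, the protocol's models ignore site, and the result is conservative tests with less power when sites differ. It is a cheap improvement of minor to moderate importance and not a threat to validity.

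At N=400 and SD 0.5 the loss at the design HR is 97.9 − 96.6 = 1.3 points for the primary endpoint and 90.1 − 87.1 = 3.0 points for alleviation by day 14. For the primary endpoint it is 64.6 − 57.2 = 7.4 points if the true HR is 1.3. At SD 0.25 or below the effect is negligible.

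The sizes depend on the assumed between-site SD, exponential recovery times, 15 sites and kits used in order. The direction was the same in both simulations.

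**What to change.** Before unblinding, prespecify in the SAP:

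- A primary Cox model stratified by site, keeping the four covariates, with small sites pooled by a fixed rule (for example, fewer than 12 patients, or 2 blocks). The threshold is a matter of choice; fixing it in advance is what counts.
- Pooled site in the logistic models for the alleviation endpoints.
- No site term for rare endpoints such as mortality. With fewer than 15 events over 15 sites, at least one site has none and its term cannot be estimated. Use site for time to hospital admission or death only if events are sufficient.
- A sentence saying that the stratified HR is a within-site effect and how it relates to the estimands in section 4.3.
- If site is left out, the reason.

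The cost is SAP wording only. If sites do not differ, stratifying the Cox model loses 98.6 − 98.2 = 0.4 points of power at N=400 and the design HR, 68.9 − 66.7 = 2.2 points at HR 1.3, and 90.3 − 88.3 = 2.0 points at an effective size of 232 (3.0 points in the second simulation, which did not pool sites).

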8.3 Blinding

Patients and investigators/study personnel will be blinded to study treatment assignment.

8.4 Treatment Compliance

The first dose of investigational product will be administered following randomization during the screening/enrollment/randomization visit and recorded by the patient in the eDiary. During the 30-day treatment period, patients will enter the dosing regimen taken (number of actuations, date, and time) BID in the eDiary. Patients should make every attempt to maintain consistency in the dosing schedule.

Qualified healthcare providers will contact patients on days 2, 4, 6, 8, 10, 12, 14, 21 ± 2 days, and 30 ± 2 days for a health status check, to collect adverse event and concomitant medication information, and to confirm/clarify information recorded in the eDiary (including treatment compliance). Based on these compliance checks, the patient may be counseled about the importance of taking the investigational product as instructed.

8.5 Investigational Product Materials and Management

8.5.1 Description of Investigational Product

Ciclesonide is a white to yellow-white powder. It is soluble in dehydrated alcohol, acetone, dichloromethane, and chloroform. The molecular formula of ciclesonide is $C_{32}H_{44}O_7$.

Ciclesonide will be supplied by the sponsor as commercially available Alvesco Inhalation Aerosol, 160 μ g. Alvesco 160 μ g Inhalation Aerosol is a pressurized, metered-dose aerosol unit fitted with a dose indicator. The 160 μ g/actuation strength contains 60 actuations fill/canister. Alvesco is intended for oral inhalation only. Each unit contains a solution of ciclesonide in propellant HFA-134a (1,1,1,2 tetrafluoroethane) and ethanol. After priming, Alvesco 160 μ g delivers 160 μ g of ciclesonide from the actuator. The actual amount of drug delivered to the lung may depend on patient factors, such as the coordination between the actuation of the device and inspiration through the delivery system.

A matching placebo MDI will also be provided.

8.5.2 Investigational Product Packaging and Labeling

Investigational product will be supplied as commercially available Alvesco Inhalation Aerosol, 160 μ g or a matching placebo MDI. Two inhalers will be provided per patient in a patient kit. The investigational product label will include the protocol number and notice that the contents are for research use only. A unique identifier on the label will provide traceability of the investigational product to the lot number, batch number, and retest date.

8.5.3 Investigational Product Storage

Investigational product should be stored per Alvesco Inhalation Aerosol labeling (ie, 25°C [77°F] with excursions permitted between 15°C and 30°C [59°F to 86°F]) (Alvesco Inhalation Aerosol US prescribing information, 2019).

Until dispensing, investigational products must be stored in a securely locked area, accessible only to authorized site personnel and the study monitor.

8.5.4 Investigational Product Handling and Disposal

The sponsor will supply investigational products only to the investigator or designee. The investigator or designee (eg, site pharmacist) is responsible for inventory, storage, and dispensing of investigational products. The investigator will not allow use of the investigational products other than as directed by this protocol.

The patient will return investigational product (ie, used and unused MDIs) to the study site during their visit on day 30 (window of + 2 days). In the event the patient is withdrawn from the study, they should be instructed to return the investigational product to the study site in a timely manner.

All used and unused MDIs must be returned to the sponsor according to instructions provided to the site by the sponsor, site monitor, or designee.

8.6 **Procedure for Breaking the Randomization Code**

Under normal circumstances, the blind will not be broken. In the event of a medical emergency, when management of a patient's condition requires knowledge of the treatment assignment, the blind may be broken. Should emergency unblinding be necessary, the investigator will contact the contract manufacturing organization for unblinding information and will notify the sponsor immediately.

Reasons for unblinding will be documented in the eSource. The date and the identity of the person responsible for breaking the blind must be also documented.

8.7 Investigational Product Accountability

The investigator must ensure that all investigational product supplies are kept in a secure locked area, under controlled temperature, with access limited to those authorized by the investigator. The investigator must maintain accurate records of the receipt of all investigational product shipped by the sponsor or the sponsor's representative, including but not limited to the date received, lot number, expiration date, amount received, and the disposition of all investigational product.

8.8 Concomitant and Prohibited Medications

Investigators may prescribe concomitant medications as standard supportive COVID-19 care.

Concomitant medications (including prescription medications, over-the-counter medications, herbal medications, vitamins, and nutritional supplements) taken by the patient and the reasons for use will be recorded during the screening/enrollment/randomization visit. Patients should continue to take these medications as directed during their participation in the study.

Concomitant medication use occurring during the 30-day treatment period will be collected by qualified healthcare providers during the scheduled patient contacts on days 2, 4, 6, 8, 10, 12, 14, 21 ± 2 days, and 30 ± 2 days and recorded in the eSource.

Patients who received treatment with inhaled or intranasal corticosteroids within 14 days or oral corticosteroids within 90 days of the screening/enrollment/randomization visit are excluded from study participation. Patients are also excluded from study participation if they are participating in any other clinical study or have used any investigational agent within 30 days of the screening/enrollment/randomization visit or if they are currently receiving treatment with hydroxychloroquine/chloroquine. These medications are also prohibited for the duration of the study.

9 ADVERSE EVENTS

9.1 Adverse Event Definition

An adverse event is any untoward medical occurrence in a patient administered a pharmaceutical product that does not necessarily have to have a causal relationship with the pharmaceutical product. An adverse event can, therefore, be any unfavorable and unintended sign, symptom, or disease temporally associated with the use of a medicinal product, whether or not related to the medicinal product. Any worsening of the patient's disease under study or other medical conditions will also be considered to be an adverse event, unless it is within the normal range of disease fluctuation for that patient.

Any new infection that occurs on study, regardless of the infecting agent (ie, viral or non-viral) should be captured as an adverse event. In these cases, the site of infection and source of culture (eg, bronchoalveolar lavage, tracheal aspirate, sputum, blood, urine) should be recorded.

9.2 Reporting of Adverse Events

Adverse events will be recorded starting with the signing of the ICF. Adverse events occurring during the screening/enrollment/randomization visit will be recorded by study personnel in the eSource. Information regarding adverse events occurring during the 30-day treatment period and post-treatment adverse events occurring during the follow-up period will be collected by qualified healthcare providers during the scheduled patient contacts and recorded in the eSource.

Investigators will review the reported adverse events on a regular basis during the course of the study. A DMC will conduct a review of blinded safety data once 100 subjects have been enrolled (see section 10.9).

9.2.1 Severity of Adverse Events

Adverse events will be graded for severity as follows:

- Mild is defined as causing no limitation of usual activities.
- Moderate is defined as causing some limitation of usual activities.
- Severe is defined as causing inability to carry out usual activities.

Severity of adverse events occurring during the screening/enrollment/randomization visit will be recorded by study personnel in the eSource. Severity information for each adverse event occurring during the 30-day treatment period and post-treatment adverse events occurring during the follow-up period will be obtained by qualified healthcare providers during the scheduled patient contacts and recorded in the eSource.

It should be noted that a severe adverse event need not be serious in nature and that a serious adverse event need not, by definition, be severe.

